Once eligibility is confirmed, subjects will be approached to obtain their authorization to access and use their health information for the research. Please see Section 14 for additional information regarding Data Management and Confidentiality.

8) Compensation to the Subjects

Subjects will not be compensated for their participation. Possible expenses to the subject's family include time spent at the clinic as well as expenses for travelling. Therefore subjects who would otherwise not be able to participate may be eligible for travel reimbursement for travel costs incurred as specified in question 25.

9) Study Timelines

We anticipate seeing 30 pilot participants in the first 18 months under consent form C. During this same time period up to an additional thirty participants and their mothers will be seen under consent form A, phases 1 and 2 of the study. During Phase 3, 50 participants and their parent/caregiver will be recruited into the clinical trial portion utilizing consent form B. In addition, 3 subjects will be recruited into phase 4, under consent form D. Phases 2,3, and 4 of the study, using consent forms A, B and D, will occur over the last 3.5 years of the project).

10) Study Endpoints

The primary outcome measure is a spoken language composite measured at baseline and at the end of treatment. Comparison of the two treatment groups on the outcome measure will be made through analysis of covariance, adjusted for baseline values on that measure using an intent-to-treat approach. Two-sided tests will be used with alpha at .05. With this sample size, power to detect a moderate effect size of 0.6 will be 80%, assuming equal standard deviations in the groups. The assumptions we are making to estimate power are conservative as evidenced by recent published tests of a parent mediated intervention for autism (Rogers et al., 2012) and a randomized controlled trial of a drug in FXS (Berry-Kravis et al., 2012), with samples sizes of 98 and 60, respectively, and behavioral outcome measures.

Analysis of our secondary outcome measure, the social avoidance subscale of the FXS- normed ABC, as well as the exploratory VAS and CGI will follow the same approach as the primary analysis. Additional analyses will examine potential child moderators of response to lovastatin (age, Leiter, ADOS symptom severity) using linear regression.

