To summarize, there will be four consent forms: one for the pilot participants who will interact with the project clinicians for the purposes of staff training (consent form C), one in Phases 1 and 2 for the purposes of collecting data on the preliminary efficacy of PILI (consent form A), one for the clinical trial during Phase 3 (consent form B) and one for the 5-8-year old cohort (consent form D). Patients who do not receive the PILI intervention in Phase 2 will be offered the opportunity to participate in Phase 3. All participants being consented under form D will be consented over the phone. Additionally, because of the young age and developmental level of these participants (consent form D), we will not be conducting assent procedures.

11 (a). Efficacy/Behavioral Assessments

Parent-Implemented Language Intervention (Consent Form Versions A, B, and D):

The parent-implemented language intervention will be delivered entirely in the participants' homes through VTC over 20 weeks. Each session will be delivered by an ASHA-certified Speech Language Pathologist (SLP) in collaboration with a Board- Certified Behavior Analyst (BCBA).

At the end of the baseline assessment procedures (described subsequently), the SLP and BCBA will provide an overview of the intervention program. The parent/caregiver will be given a MacBook Pro laptop computer and tablet with preinstalled VTC software (e.g., Skype). Project staff will demonstrate use of VTC software and arrange a time for a practice session once the family returns home. The first VTC intervention session will be scheduled within 5 weeks of baseline. VTC support will be provided by the Administrative Core.

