ix. Child Spoken Language: ICF A and B

The conversation and narration procedures described in Preliminary Studies will be administered at the baseline and post-treatment visits. Alternate versions of conversation and narration materials will be administered at the two visits and counterbalanced.

Neurobehavioral Analysis Core staff blind to hypotheses and participant characteristics will transcribe/code. A spoken language ability composite will be obtained for each assessment time by taking a weighted mean of variables reflecting talkativeness, fluency, intelligibility, vocabulary diversity, and syntactic complexity in combined narrative and conversational samples. This composite will provide a broad-based and robust measure of spoken language ability and serve as the primary outcome measure. Exploratory analyses will evaluate the separate contributions of the variables included in the composite (30 min).

DOS 5.1 (Version Date: 07-Nov-2017)

x. The Social Communication Questionnaire (SCQ): ICF D

A widely used informant report checklist that evaluates communication and social skill deficits common to those with symptoms of autism. This brief questionnaire will be completed by the participant's parent/caregiver (10 min).

xi. The Vineland Adaptive Behavior Scales (VABS): ICF D

The VABS is a widely used informant report checklist that will be used to assess four domains: communication; self-care; social skills; and maladaptive behavior. It will be completed by the participant's parent/caregiver (30 min).

xii. Childhood Autism Rating Scale, Second Edition (CARS-2): ICF D

An examiner completed behavioral rating scale used to evaluate symptoms of autism following a direct observation of a child. The parent-child structured interaction will be used as the context which is evaluated for this measure.

xiii. The Aberrant Behavior Checklist (ABC): ICF A, B, and D

A behavior rating scale completed by the parent/caregiver that is frequently used to examine treatment effects on challenging behaviors for individuals with FXS. The scale is comprised of 58-items in the following domains: (1) irritability, agitation, crying; (2) lethargy, social withdrawal; (3) stereotypic behavior (4) hyperactivity, noncompliance; and (5) inappropriate speech (15 min). The Sansone et al. (2011) FXS-normed ABC scoring measures will be used. The social avoidance subscale score will be a secondary clinical endpoint.

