i. The Clinical Global Impressions Scale–Severity (CGI-S) and Improvement (CGI-I) (Busner & Targum, 2007): ICF B

These standardized assessment instruments are widely used in drug trials to enable the clinician to utilize history from the parents or caregiver and incorporate it into a clinical rating, first for severity, and then for clinical follow-up. The CGI-S will be used at the pre-treatment assessment to judge symptom severity and the CGI- I will be used at the 3 month and 6 month visits.

ii. The Visual Analogue Scale (VAS): ICF B

The measure will be used to assess parental impressions of progress in two key symptoms: spoken language impairment and social impairment. The distance of the mark from one end is used as the outcome variable for analysis. The VAS will be administered at each visit. The VAS has been effectively used as an outcome measure in other FXS drug trials (Erickson et al., 2011; Paribello et al., 2010; [name] et al 2013).

11 (b). Medical/Safety Assessments (Consent Form B):

The schedule of procedures is also listed in a table format below:

Assessment	Screening/Baseline Visit 1 (Week 1, Day 0)	Visit 2 (Week 10 ± 3 Days)	Visit 3 (Week 20 ± 3 Days)	
Informed Consent	X			
Inclusion/Exclusion Criteria	X			
Medical History	X			
Vital Signs	X	X	X	
Physical Exam	X	X	X	
Neurological Exam	X	X	X	

For IRB Use

Document Revision Date: July 12, 2013

Concomitant Medications	X	X	X
Adverse Events	X	X	X
Clinical Labs	X	X	X
Biomarkers	X	X	X
Leiter-R (45 min.)	X		
ADOS-2 (45 min.)	X		
CGI-S	X		
CGI-I		X	X
VAS	X	X	X
Language Assessments			
CELF-4 (15 min.)	X		X
CASL (45 min.)	X		X
TROG-2 (10 min.)	X		X
PPVT-4 (10 min.)	X		X
EVT-2 (10 min.)	X		X
FACB (45 min.)	X		
Child Spoken Language (30 min.)	X		X
Parent Narrative Task 1 (15 min.)	X		X
Parent Narrative Task 2 (15 min.)	X		X
Parental Assessments			
K-BIT-2 (maternal) (25 min.)	X		
Parent Questionnaires			
ABC (15 min.)	X	X	X
ADAMS (10 min.)	X	X	X
RBS-R (10 min.)	X	X	X
PSI (10 min.)	X		X
PSOC (10 min.)	X		X
Family Background	X		
Questionnaire (10 min.)			
SCL-90 (maternal) (10 min.)	X		X
Post Treatment Survey			X
Dispense Medication	X	X	

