Randomization to lovastatin or placebo will be conducted by the UCDMC pharmacy using a computer algorithm. IDS will over-encapsulate the active study medications and prepare the placebo capsules prior to dispensing. Equivalence of the groups on these stratification variables, as well as other variables (e.g., child autism symptom severity and maternal IQ), will be tested, with any significant differences accounted for by inclusion of covariates in the primary analyses.

The dose will range from 10 to 40 mg of lovastatin or placebo depending on tolerance of the dose. The dose will start at 10 mg per day and will be increased by 10 mg increments on a weekly basis from study weeks 1 through 4 as listed below. Dosing will occur once per day in the evening. Dose tolerance will be assessed through a weekly phone call or email contact conducted by a study physician during the titration period and a dose decrease can be made if necessary. If a dose decrease is made between weeks 2 and 4 no further dose titrations will occur and subject will be considered on a stable dose throughout the remainder of the titration period and study.

If more than one dose change is needed, the subject will be discontinued from the study. Once a stable dose is reached, subjects will remain at the designated dose through visit 3 and will be contacted approximately every other week by study staff to assess for possible adverse events and verification of proper dosing. Study participants will be dispensed study medication at visits one and two and will discontinue dosing after completing visit 3.

Week 1: 10 mg (Day 1-7) Week 2: 20 mg (Day 8-14) Week 3: 30 mg (Day 15-21) Week 4: 40 mg (Day 22- 28) Week 5-20: 40 mg or OTD (Day 29- 140)

Our dosage model takes into consideration the biphasic and pleiotropic effects of statins. The biphasic effect can be explained by the higher affinity for the enzymes that catalyze non-sterol product formation than for the cholesterol biosynthesis enzymes. Low doses of statins mainly affect cholesterol synthesis, while high doses affect mevalonate-derivative intermediates, which are essential for the prenylation of proteins and Ras activation (Li, et al., 2007). The pleiotropic effects of statins suggest that the sustained use of statins (more than 2 weeks) causes PTEN up regulation, which inhibits the PIK3/AKT pathway; and that higher acute dose administration of statins will inhibit Ras, which is our targeted effect. (Ludman, et al., 2009).

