Adverse events (AE) will be documented along with any changes in study medication dose or use of other medications. Each AE will be scored for severity, frequency, and relatedness to lovastatin. All serious adverse events will be reported to our IRB as required by reporting guidelines. The DSMB will also review the study data and assess for safety on a regular basis.

Safety labs, listed below, will be conducted at all three visits through the UC Davis health system pathology laboratory. These laboratory tests will assess for creatine phosphokinase (CPK) as rare irritation to the muscle have been reported with statin treatment. The liver function studies will be utilized to rule out irritation to the liver and the urinalysis will screen for rhabdomyolysis. The lipid panel will assess that cholesterol and triglycerides remain within the normal range. Due to the processing requirements for the lipid panel, blood draws will be done while subjects are fasting. If there is any sign of myopathy, muscle pain or allergic reaction the medication will be discontinued. Pregnancy testing will only be conducted on female participants of child-bearing potential.

Safety Lab Tests

Chemistry	Hematology	Urinalysis
Creatine Kinase	Hemoglobin	pH
Potassium	Hematocrit	Color
Chloride	WBC	Clarity
Carbon Dioxide	RBC	Specific Gravity
BUN	MCV	Occult blood
Creatinine	MCH	Urobilinogen
Glucose	MCHC	Ketones

Calcium	RDW	Protein
Protein	MPV	Glucose
Albumin	Platelet Count	Pregnancy spot urine
ALP	Neutrophils	
AST	Lymphocytes	
ALT	Monocytes	
Bilirubin	Eosinophil	
Cholesterol	Basophils	
HDL cholesterol		
Triglycerides		
Serum Pregnancy (βHCG)		

In addition to the 7ml of blood for safety labs, we will collect approximately 30 ml of blood at each visit for biomarker analysis of immune function, MEK/ERK, RhoGTPase, and Ca2+ signaling, and cell activation.

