The investigator has the right to discontinue or withdraw a subject from the study at any time. In addition, subjects have the right to voluntarily discontinue study drug or withdraw from the study at any time for any reason. Reasons for discontinuation of study drug or withdrawal from the study may include, but are not limited to, the following:

- Subject withdrawal of consent at any time
- Any medical condition that the investigator determines may jeopardize the subject's safety if he continues in the study

DOS 5.1 (Version Date: 07-Nov-2017)

- Investigator determines it is in the best interest of the subject
- Subject non-compliance

Discontinuation from Study Drug:

Subject must discontinue study drug if they experience any of the following:

- Hematological events
- Subject unable to continue to comply with study requirements

Subjects who discontinue study drug prematurely will be asked to return to the clinic for a study completion/early termination visit and may undergo follow up assessments. The primary reason for premature study drug discontinuation should be documented on the appropriate eCRF.

Withdrawal from Study:

Every effort should be made to obtain information on subjects who withdraw from the study. The primary reason for withdrawal from the study should be documented on the appropriate eCRF. Subjects will not be followed for any reason after consent has been withdrawn.

16) Risks to Subjects

Venipuncture:

The risks of blood collection from a vein include discomfort at the site of the needle stick, possible bruising and swelling around the site of the needle stick, rarely an infection or blot clot, and uncommonly feeling faint or dizzy from the procedure. Due to the type of safety labs being conducted for this study, fasting blood draws are required, which may cause discomfort to the subject.

Privacy:

There may also be risks to subjects' privacy. Study staff at the MIND Institute will store study records and other information in a secure location and will grant access only to those who require it. However, even these safeguards cannot guarantee absolute protection of the data.

Unidentified or unforeseen risks:

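### A child who leaves under the dose-change rule, or stops drug, need not give the week-20 language sample that the intent-to-treat analysis relies on (minor)

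*Combined protocol and SAP*

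**What the plan says.** **Exit rule.** Section 11(b), in the dosing text: "If more than one dose change is needed, the subject will be discontinued from the study".

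**Drug-stop rule.** The same section, in the safety laboratory text: "If there is any sign of myopathy, muscle pain or allergic reaction the medication will be discontinued". This stops the medication and does not mention leaving the study.

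**Analysis.** Section 10 compares the arms by ANCOVA "adjusted for baseline values on that measure using an intent-to-treat approach".

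**When the outcome is measured.** Section 11(a), Child Spoken Language, says the procedures "will be administered at the baseline and post-treatment visits". In the schedule in section 11(b), the row "Child Spoken Language (30 min" min.) is marked at Visit 1 and at Visit 3 (week 20 ± 3 days). It is not marked at Visit 2, and the schedule has no early termination column.

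**Follow-up.** Section 15 says that "subjects have the right to voluntarily discontinue study drug or withdraw from the study at any time for any reason". It then treats stopping drug and withdrawing under separate subheadings. The drug-stop part begins "Subject must discontinue study drug if they experience any of the following" and lists hematological events and inability to comply. Children who stop drug early are asked back for a completion or early termination visit, and follow-up assessments are permitted. For those who withdraw, staff are to try hard to obtain information. Follow-up is barred only once consent is withdrawn.

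**Start of PILI.** Section 11(a): "The first VTC intervention session will be scheduled within 5 weeks of baseline".

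**The concern.** An intent-to-treat comparison needs an end-of-treatment value from the children as randomised. Here, needing a second dose change ends participation, and tolerance is something the drug can affect. If tolerance partly decides who has a week-20 language value, the children compared are no longer quite the two randomised groups. There is no mid-study language sample to fall back on, and the text gives no method for missing outcomes.

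The early termination visit does not close the gap. It is a request, its content is not listed, and it is not tied to week 20. A sample taken there would follow less PILI than a Visit 3 sample, and the plan does not say whether it would enter the primary analysis. Hypothesis 1b is exposed in the same way, because section 10 regresses the 20-week child outcome on parent behaviour.

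At stake are a few primary outcomes in a trial of 50 children. They could be collected at a visit that is already scheduled, and once missed they cannot be recovered.

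**Working it through.** **1. The text.** For each way off treatment, what is required?

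| Route | Where | Visit | Week-20 language sample required? |
|---|---|---|---|
| More than one dose change | 11(b) | None named; section 15 asks only for effort to obtain information on those who withdraw | No |
| Myopathy, muscle pain or allergic reaction | 11(b) | Section 15 drug-stop route: early termination visit requested, assessments optional | No |
| Consent withdrawn | 15 | Follow-up barred | Not applicable |

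The first two rows carry the point. Neither involves withdrawal of consent, so section 15 would allow the sample; it does not require it.

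**2. The plan's own power figure, as a reference.** Section 10 states 80% power for an effect of 0.6 at two-sided 0.05. Sections 4 and 17 give 50 children with half on lovastatin, so 25 per arm. With no covariate, the noncentrality is 0.6 / √(1/25 + 1/25) = 0.6 / 0.283 = 2.12. Power is then 55% (t) or 56% (normal), so 80% is not reproduced. It is reached only if ANCOVA is credited with a baseline correlation of about 0.65 to 0.67, which the documents do not state. That is a separate matter and is not evidence for this point. It does mean that the loss should be shown over a range of correlations r.

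**3. Power after loss.** Loss counts are assumed. Noncentrality = 0.6 / √[(1 − r²)(1/n₁ + 1/n₂)]. Degrees of freedom are N − 2 unadjusted and N − 3 for ANCOVA.

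| Children with a value | No covariate | r = 0.5 | r = 0.7 |
|---|---|---|---|
| 25 v 25 | 0.547 | 0.670 | 0.829 |
| 24 v 25 | 0.538 | 0.660 | 0.821 |
| 24 v 24 | 0.530 | 0.651 | 0.813 |
| 23 v 24 | 0.521 | 0.641 | 0.804 |

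The drop is about 1 to 3 points in every column.

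**4. Shift in a completer comparison.** Assume tolerance is standard normal and has correlation ρ with the residual outcome, and that the least tolerant fraction d of an arm is lost. The mean of those kept is ρ·φ(z_d)/(1 − d), and the shift is lovastatin minus placebo. At d = 1/25 the factor is 0.0898; at d = 2/25 it is 0.1616. Take ρ from 0.3 to 0.5.

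- 1 v 1 lost: 0.
- 1 v 0 lost: 0.0898ρ = 0.027 to 0.045 residual SD. The standard error is √(1/24 + 1/25) = 0.286, so the ratio is 0.09 to 0.16.
- 2 v 1 lost: (0.1616 − 0.0898)ρ = 0.022 to 0.036. The standard error is √(1/23 + 1/24) = 0.292, so the ratio is 0.07 to 0.12.

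Removing exactly the least tolerant of 25 by simulation gives slightly less: 0.024 to 0.040 (1 v 0) and 0.020 to 0.035 (2 v 1). Hence about 0.04 SD at most for these splits.

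That limit depends on the split. If all three losses fell in one arm (d = 3/25, factor 0.2273), the shift would be 0.2273ρ = 0.068 to 0.114 SD, or 0.23 to 0.39 of a standard error of √(1/22 + 1/25) = 0.292. Reversing the sign of ρ or of the imbalance reverses the shift.

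**5. Timing.** Titration runs to day 28 of 140 (section 11(b)). The first PILI session may be as late as 5 × 7 = day 35 (section 11(a)). A child who stops during titration and is seen promptly could therefore be sampled before any PILI session. This is an extreme case.

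**The case against.** **Follow-up is already provided for in part.** This stands as mitigation. Section 15 requests a visit, permits assessments and closes contact only after consent is withdrawn. Because it names the visit as a completion visit, the full Visit 3 battery may be intended. But intention is not a requirement, and neither the content nor the timing is stated.

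**Is the child's status contradictory?** A reader might infer that the plan leaves it open whether this child has left the study or only stopped drug, since section 15 separates the two and its mandatory drug-stop list omits the dose-change rule. The documents do not support that reading well. Section 15 opens by giving the investigator power to discontinue, or to withdraw, a child from the study, so it uses discontinuing for study exit too. The drug-stop list covers drug stops only, and the general list of reasons is expressly not exhaustive. Study exit is the natural meaning. Children whose medication is stopped for myopathy, muscle pain or allergic reaction clearly follow the drug-stop route.

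**The effect may be negligible.** This largely stands. Section 16 describes lovastatin as generally well tolerated, and every loss count and correlation above is assumed. The pre-PILI sample needs an early stop, a prompt visit, a language sample that is not required there, and a PILI start near its upper limit.

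**Conclusion.** The point holds as a minor one. Followed as written, the plan can lose or mistime primary outcomes for tolerance-related reasons, while promising an intent-to-treat analysis of an outcome measured only at baseline and week 20.

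The size is probably small. With 1 to 3 of 50 children lost, power falls by about 1 to 3 points. The shift is about 0.04 SD or less if losses differ by at most one child between arms, and larger if they all fall in one arm. These figures rest on assumed loss counts, a tolerance-outcome correlation of 0.3 to 0.5 and baseline correlations of 0.5 and 0.7.

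A reader might go further and infer that the treatment comparison will be biased, or biased in favour of lovastatin. The documents give no loss rate, no difference between arms and no direction, so that does not follow. The case for change rests on the unprotected endpoint and the low cost of protecting it.

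**What to change.** 1. Reconcile the dose-change rule in section 11(b) with sections 10 and 15 so that stopping study drug does not by itself end outcome collection. This would change the literal effect of the exit rule on follow-up. No view is taken on the dosing or stopping rule itself.
2. State that the Visit 3 language sample and parent measures are collected at week 20 ± 3 days from every randomised child whose consent has not been withdrawn, on or off drug, and are analysed as randomised.
3. State whether PILI sessions continue after a drug stop. If they do not, the week-20 value reflects less PILI as well as less drug, and readers need to know that.
4. List the content of the early termination visit, and say that a language sample taken there is not used as if it were the week-20 value. Name in advance how values still missing are handled; the method is the sponsor's choice.

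The cost is a short amendment and some retention effort, since Visit 3 is already scheduled. A few families who have stopped drug would still have to travel, possibly far, because section 7 allows nationwide recruitment. Section 25 reimburses travel for eligible families who could not otherwise take part.
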